#### 5.2.4 Prophylaxis medications

The following medications are recommended as prophylaxis during the first 4 cycles of treatment due to an increased incidence of Shingles and infection noted on patients in this trial:

- Shingles prophylaxis: Valtrex 500mg OD is preferred otherwise acyclovir 400mg bid can be used

- Infection prophylaxis: Ciprofloxacin or Moxifloxacin

The prophylaxis recommendations above are an additional care measure while determination as to whether there is reasonable possibility, that Trametinib and GSK2141795 caused the increased incidence of shingles or infection (urinary tract or upper respiratory) noted in the patients on this trial.

### 5.3 Duration of Therapy

In the absence of treatment delays due to adverse event(s), treatment may continue until one of the following criteria applies:

- Disease progression,
- Intercurrent illness that prevents further administration of treatment,
- Unacceptable adverse event(s),
- Patient decides to withdraw from the study,
- General or specific changes in the patient's condition render the patient unacceptable for further treatment in the judgment of the investigator,
- Clinical progression,
- Patient non-compliance
- Pregnancy
  - All women of child bearing potential (WOCBP) should be instructed to contact the investigator immediately if they suspect they might be pregnant (*e.g.*, missed or late menstrual period) at any time during study participation. Institutional policy and local regulations should determine the frequency of on study pregnancy tests for WOCBP enrolled in the study.
  - The investigator must immediately notify CTEP in the event of a confirmed pregnancy in a patient participating in the study.
- Termination of the study by sponsor.

### 5.4 Duration of Follow Up

Patients will be followed for 4 weeks after removal from study treatment or until death, whichever occurs first. Adverse event(s) related to study treatment will be followed until resolution to a  $\leq$  grade 1 or until the adverse event remains stable at the same grade for at least 2 months.

### 5.5 Criteria for Removal from Study

Patients will be removed from study when any of the criteria listed in Section 5.3 applies. The reason for study removal and the date the patient was removed must be documented in the Case Report Form.

## 6 DOSING DELAYS/DOSE MODIFICATIONS

### 6.1 Trametinib and/or GSK2141795 Dose Modifications

The table below outlines the dose levels to be used for any necessary trametinib dose modifications when dosing trametinib as a single agent:

Dose Level	Trametinib Dose/Schedule
0	2 mg QD
-1	1.5 mg QD
-2	1 mg QD

If GSK2141795 is added for disease progression after 2 cycles or because of failure to achieve a PR after 4 cycles then the dose of trametinib will be reduced to 1.5 mg and combined with 50 mg pf GSK2141795 administered daily.

The table below outlines the dose levels to be used for any necessary trametinib dose modifications when trametinib is dosed with GSK2141795:

Dose Level	Trametinib Dose/Schedule
0	1.5 mg QD
-1	1.0 mg QD
-2	0.5 mg QD

The table below outlines the dose levels to be used for any necessary GSK2141795 dose modifications:

Dose Level	GSK2141795 Dose/Schedule
0	50 mg QD
-1	25 mg QD

A maximum of two Trametinib and/or one GSK2141795 dose level reductions are allowed. Patients may have up to 2 dose level reductions of Trametinib while taking Trametinib alone (lowest dose allowed is 1 mg QD). Patients may have a further 2 dose level reductions of Trametinib while taking Trametinib in combination with GSK2141795 (lowest dose allowed is 0.5 mg QD).

6.1.1 Trametinib or GSK2141795 Dose Modification for Toxicities Hematological/ Non-Hematological Toxicities Not Otherwise Specified in Subsequent Sections

The investigator should use clinical judgment to determine which drug may be contributing to the toxicity necessitating dose adjustment and make the appropriate change for that drug.

Study Drug(s) Modification for Clinically Significant Toxicities Deemed Related to Study Drug(s) (This section is not for specific AEs such as hypertension, rash, ejection fraction changes, pneumonitis, diarrhea, liver chemistry, QTc prolongation, visual changes, neutropenia, or thrombocytopenia. Refer to other sections for these specific AEs).		
CTCAE v4 Grade	Management Guideline	Dose Modification
Grade 1	Monitor as clinically indicated. Provide supportive care according to institutional standards	Continue trametinib and/or GSK2141795 at current dose level.
Grade 2		
 
• Interrupt trametinib and/or GSK2141795 until resolution to grade 1 or baseline.
 
• Upon resolution, restart trametinib and/or GSK2141795 at current dose level.
 

Grade 3		
 
• Interrupt trametinib and/or GSK2141795 until resolution to grade 1 or baseline.
 
• Upon resolution to baseline or grade 1, restart the interrupted agent(s) with one level of dose reduction
 
• If the Grade 3 toxicity recurs, interrupt trametinib and/or GSK2141795; When toxicity resolves to Grade 1 or baseline, restart the interrupted agent(s) reduced by another dose level
 

Grade 4		Permanently discontinue trametinib and/or GSK2141795.
Study drug(s) should be discontinued if treatment delay is $\geq 28$ days due to toxicities. If the investigator concludes that continued study drug(s) will benefit a patient, the study chair and CTEP Medical Monitor may be consulted for the possibility of resuming study drug(s), provided that toxicities have resolved to baseline or grade 1.		

6.1.2 Trametinib and/or GSK2141795 Dose Modification for Rash

Rash is a frequent AE observed in patients receiving trametinib (Investigator’s Brochure, 2012a) or GSK2141795. Recommendations for supportive care and guidelines for dose modifications for rash are based on experience with other MEK inhibitors and EGFR inhibitors (Balagula *et al.*, 2010; Lacouture *et al.*, 2011).

Further, two types of rashes may be seen with the trametinib + GSK2141795 combination:

- Acneiform rash, typically associated with trametinib.
- Maculopapular rash, often associated with pruritus GSK2141795.

If the diagnosis is unclear, a biopsy and photographs should be obtained as well as a dermatology consult.

In general, topical and oral antibiotics play a larger role in management of the trametinib acneiform rash, while topical and oral steroids are more relevant to the management of the GSK2141795 maculopapular rash. Subjects should contact the investigator immediately upon onset of a rash. Full supportive care should be provided to subjects who experience a rash while on study. The following information is a guideline.

The institutional standards for the management of skin-related AEs can differ from these guidelines. In this case, best clinical judgment should be applied and a consultation with the study chair or the CTEP Medical Monitor may be required.

**Guidelines for Supportive Care of Rash**

Type of Care	Action
Prevention/ Prophylaxisa	
 
• Avoid unnecessary exposure to sunlight.
 
• Apply broad-spectrum sunscreen (containing titanium dioxide or zinc oxide) with a skin protection factor (SPF) <math>\geq 15</math> at least twice daily.
 
• Use thick, alcohol-free emollient cream (e.g., glycerine and cetomacrogol cream) on dry areas of the body at least twice daily.
 
• Topical steroids and antibiotics should be applied at least twice daily, starting on Day 1 of study treatment, to body areas such as face, chest, and upper back.
 
• Use mild-strength topical steroid (hydrocortisone 1% cream) or topical antibiotic (e.g., clindamycin) or oral antibiotics (e.g., doxycycline 100 mg BID, minocycline 100 mg BID).
 

Symptomatic Careb	
Upon the first signs of rash, mild strength topical steroid (e.g. hydrocortisone 1% cream) with escalation to higher strength and/or oral steroid as detailed below.
 
 
• Upon the first signs of papulopustular (acneiform) rash consider doxycycline (100 mg BID) or minocycline (100 mg BID).
 
• Pruritic lesions: Cool compresses and oral antihistamine therapies.
 
• Fissuring lesions: Monsel’s solution, silver nitrate, or zinc oxide cream.
 
• Desquamation: Thick emollients and mild soap.
 
• Paronychia: Antiseptic bath and local potent corticosteroids in addition to antibiotics; if no improvement, consult dermatologist or surgeon.
 
• Infected lesions: Appropriate bacterial/fungal culture-driven systemic or topical antibiotics.
 
• For subjects who had study drug reduced because of rash, re-escalation may be considered if toxicity does not recur with a re-challenge at a lower dose.
 

a Rash prophylaxis is recommended for the first 6 weeks of study treatment.
	

b Patients who develop rash/skin toxicities should be seen by a qualified physician and should receive evaluation for symptomatic/supportive care management.
	

Study Drug(s) Dose Modification Guidelines and Management for Rash		
Rash Severity	Management Guideline	Dose Modification
Grade 1	
 
• Initiate prophylactic and symptomatic treatment measures.
 
• Use moderate strength topical steroid.
 
• Reassess after 2 weeks.
 
	
 
• Continue trametinib and/or GSK2141795.
 
• If rash does not recover to baseline within 2 weeks despite best supportive care, reduce trametinib and/or GSK2141795 by one dose level.
 

Grade 2	
 
• Initiate prophylactic and symptomatic treatment measures.
 
• Use moderate strength topical steroid.
 
• Reassess after 2 weeks.
 
	
 
• Reduce trametinib and/or GSK2141795 by one dose level.
 
• If rash recovers to <math>\leq</math> grade 1 within 2 weeks, increase dose to previous dose level.
 
• If no recovery to <math>\leq</math> grade 1 within 2 weeks, interrupt trametinib until recovery to <math>\leq</math> grade 1.
 
• Restart trametinib and/or GSK2141795 at reduced dose level.
 

Grade <math>\geq</math>3	
 
• Use moderate strength topical steroids PLUS oral methyl-prednisolone dose pack.
 
• For papulopustular (acneiform) rash consider doxycycline 100 mg bid or minocycline 100 mg bid.
 
• Consult dermatologist.
 
	
 
• Interrupt trametinib and/or GSK2141795 until rash recovers to <math>\leq</math> grade 1.
 
• Restart with trametinib and/or GSK2141795 reduced by one dose level.
 
• If no recovery to <math>\leq</math> grade 2 within 28 days, permanently discontinue trametinib and/or GSK2141795.
 

1. Rash prophylaxis is recommended for the first 6 weeks of study treatment.                  2. Moderate-strength topical steroids: Hydrocortisone 2.5% cream or fluticasone propionate 0.5% cream.                  3. Approval of CTEP Medical Monitor is required to restart study treatment after <math>\geq</math>28 days of interruption.                  4. Trametinib may be escalated to previous dose level if no rash is evident 4 weeks after restarting study treatment.
		

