#### **Cutaneous AEs**

Rash may or may not be associated with pruritis. Preliminary data suggest that drug interruption and dose reduction upon re-challenge ameliorate the symptoms. Rash management should focus on symptom relief and maintenance of an intact integument. Dermatology consult is recommended when clinically appropriate. Topical steroid creams have been found to provide some relief from symptoms. Treatment will be dose reduced or discontinued for clinically significant toxicity not adequately controlled by supportive care measures.

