7.1.1.2 CAEPR for GSK2141795 (NSC 767034)

The Comprehensive Adverse Event and Potential Risks list (CAEPR) provides a single list of reported and/or potential adverse events (AE) associated with an agent using a uniform presentation of events by body system. In addition to the comprehensive list, a subset, the Specific Protocol Exceptions to Expedited Reporting (SPEER), appears in a separate column and is identified with bold and italicized text. This subset of AEs (SPEER) is a list of events that are protocol specific exceptions to expedited reporting to NCI via CTEP-AERS (except as noted below). Refer to the 'CTEP, NCI Guidelines: Adverse Event Reporting Requirements' [http://ctep.cancer.gov/protocolDevelopment/electronic\\_applications/docs/aeguidelines.pdf](http://ctep.cancer.gov/protocolDevelopment/electronic_applications/docs/aeguidelines.pdf) for further clarification. Frequency is provided based on 150 patients. Below is the CAEPR for GSK2141795.

NOTE: Report AEs on the SPEER ONLY IF they exceed the grade noted in parentheses next to the AE in the SPEER. If this CAEPR is part of a combination protocol using multiple investigational agents and has an AE listed on different SPEERs, use the lower of the grades to determine if expedited reporting is required.

Version 2.1, July 26, 2013

Adverse Events with Possible Relationship to GSK2141795 (CTCAE 4.0 Term) [n= 150]			Specific Protocol Exceptions to Expedited Reporting (SPEER)
Likely (>20%)	Less Likely (<=20%)	Rare but Serious (<3%)	
GASTROINTESTINAL DISORDERS			
Diarrhea			Diarrhea (Gr 2)
	Esophagitis		
	Gastrointestinal mucositis 		
Nausea			Nausea (Gr 2)
Vomiting			Vomiting (Gr 2)
GENERAL DISORDERS AND ADMINISTRATION SITE CONDITIONS			
Fatigue			Fatigue (Gr 2)
METABOLISM AND NUTRITION DISORDERS			
Anorexia			Anorexia (Gr 2)
	Hyperglycemia		Hyperglycemia (Gr 2)
	Hypoglycemia		
RESPIRATORY, THORACIC AND MEDIASTINAL DISORDERS			
	Respiratory mucositis 		
SKIN AND SUBCUTANEOUS TISSUE DISORDERS			
	Rash maculo-papular		

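### The grade 2 rash row reduces and restarts trametinib and/or GSK2141795 but interrupts only trametinib, leaving the hold of GSK2141795 undirected in combination patients

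*Combined protocol and SAP*

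**What the plan says.** Section 6.1.2 is titled for both agents. It describes two rash types on the combination: an acneiform rash attributed to trametinib, and a second type given as "Maculopapular rash, often associated with pruritus GSK2141795". It then gives a dose-modification table by grade.

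The grade 2 row first reduces trametinib and/or GSK2141795 by one dose level. If the rash recovers within 2 weeks, the dose goes back up. If it does not, the instruction is "grade 1 within 2 weeks, interrupt trametinib until recovery to" grade 1 or less. The row ends with "Restart trametinib and/or GSK2141795 at reduced dose level".

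The corresponding line for grade 3 or higher is "Interrupt trametinib and/or GSK2141795 until rash recovers to" grade 1 or less.

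On rash from GSK2141795, section 2.2.2 (Cutaneous AEs) says: "Preliminary data suggest that drug interruption and dose reduction upon re-challenge ameliorate the symptoms". The adverse event list for that agent in section 7.1.1.2 includes "Rash maculo-papular".

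**The concern.** The interruption step is the only bullet in the table that names trametinib alone. For a patient on trametinib monotherapy that is correct. For a patient on the combination, the row does not say what to do with GSK2141795 while the rash remains grade 2, and then gives a restart rule for it.

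The gap matters most when the investigator attributes the rash to GSK2141795. That agent has a single reduced level, 25 mg: "A maximum of two Trametinib and/or one GSK2141795 dose level reductions are allowed". If it was already reduced at the first step, interruption is the next action available, and it is the one the row leaves out. The grade 2 row also has no discontinuation rule, so while the rash stays at grade 2 the row never directs a stop of GSK2141795. Meanwhile the patient loses trametinib, and restarting after 28 days or more of interruption needs Medical Monitor approval.

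What is at stake is combination-phase safety and dosing, and consistent handling across sites.

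**Working it through.** No formula applies, and the plan gives no figure to reproduce. The check is a line-by-line comparison of the rash table, followed by a search for text elsewhere that would supply the missing instruction.

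**Drugs named in each dose-modification bullet**

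| Row | Action | Drugs named |
|---|---|---|
| Grade 1 | Continue | Trametinib and/or GSK2141795 |
| Grade 1 | Reduce if not back to baseline in 2 weeks ("reduce trametinib and/or GSK2141795 by one dose level") | Trametinib and/or GSK2141795 |
| Grade 2 | Reduce | Trametinib and/or GSK2141795 |
| Grade 2 | Return to previous dose if recovered | None named |
| Grade 2 | Interrupt if not recovered in 2 weeks | **Trametinib only** |
| Grade 2 | Restart at reduced level | Trametinib and/or GSK2141795 |
| Grade 3 or higher | Interrupt | Trametinib and/or GSK2141795 |
| Grade 3 or higher | Restart at reduced level | Trametinib and/or GSK2141795 |
| Grade 3 or higher | Discontinue if not at grade 2 or less in 28 days | Trametinib and/or GSK2141795 |

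Bullets that name a drug: 2 + 3 + 3 = 8. Seven cover both agents and one covers trametinib alone. Outside the bullets, footnote 4, attached to the grade 3 or higher restart, permits re-escalation of trametinib only.

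**Does the omission look deliberate?** Where the protocol intends a trametinib-only rule it titles the section that way (6.1.3, 6.1.6, 6.1.7, 6.1.9). Section 6.1.2 is titled for both agents. No reason is given for holding trametinib alone at grade 2 but either or both agents at grade 3. The restart line presupposes that GSK2141795 could have been held.

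**Does other text fill the gap?**

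- Section 6.1.1 tells the investigator to judge which drug is contributing, but it covers toxicities not specified elsewhere and its table expressly excludes rash.
- The clinical-judgment sentence in section 6.1.2 applies where institutional standards differ from the guideline. It does not tell a site following the table which drug to hold.
- The last sentence of the Cutaneous AEs paragraph in section 2.2.2 allows treatment to be reduced or discontinued for significant rash that supportive care does not control. This gives background authority to stop GSK2141795, but it is not the grade 2 interruption rule.

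**Literal dose path.** A combination patient starts at trametinib 1.5 mg and GSK2141795 50 mg daily. Suppose GSK2141795 is reduced to 25 mg and the rash is still grade 2 at two weeks. The row then takes trametinib to 0 mg and says nothing about the 25 mg of GSK2141795.

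**How many patients?** Section 2.2.1.5 reports rash in 22% of 23 combination patients, 0.22 × 23 ≈ 5. Neither rash type nor grade is given, so the number who would reach this step cannot be estimated.

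**The case against.** The strongest reply is that this is an omitted phrase whose meaning is recoverable. The row never orders GSK2141795 to continue, and the restart line shows that a hold was contemplated. The section calls its content a guideline and asks for biopsy, photographs and a dermatology consult when the diagnosis is unclear. Section 2.2.2 permits reduction or discontinuation for uncontrolled rash, section 5.3 allows treatment to end for unacceptable events, and worsening to grade 3 brings in a row that covers both agents. All of this stands and limits the consequence. It does not make the line right: a site working from the table still reaches a step that names one drug and omits the other.

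A reader might go further and infer that the row makes sites hold the wrong drug. The documents do not support that. Section 7.1.1.1 lists rash as likely (>20%) with trametinib, and its footnote includes macular, papular and generalized forms. Section 7.1.1.2 puts maculopapular rash in the less likely (<=20%) column for GSK2141795. Section 6.1.2 describes an association, not an exclusive cause.

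A reader might also multiply the daily GSK2141795 dose by an assumed length of hold, or compute how much drug would have cleared. The documents fix no length of hold and do not link drug level to rash resolution, so such figures would not measure harm.

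**Conclusion.** The inconsistency is real and confined to the grade 2 interruption line. That line conflicts with the row's own restart line, with the interruption line for grade 3 or higher, and with the statement in section 2.2.2 on what helps GSK2141795 rash. On a literal reading, a combination patient whose persistent grade 2 rash is attributed to GSK2141795 has trametinib held and is not directed to stop GSK2141795.

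The conclusion assumes a patient on the combination and a site that follows the table as written. It does not apply to monotherapy. The size of any harm cannot be stated from the documents. No effect is claimed on the primary response rate, the sample size or any analysis; response on the combination is a secondary objective with its own baseline. It is an operative dosing rule that should be corrected, at a modest level of seriousness.

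**What to change.** Change the grade 2 line to read: if no recovery to grade 1 or less within 2 weeks, *interrupt trametinib and/or GSK2141795 until recovery to grade 1 or less*.

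Add one sentence, because and/or alone does not say which drug to hold: the investigator holds the agent or agents judged to contribute, guided by the rash types already described in section 6.1.2 (acneiform pointing to trametinib, maculopapular to GSK2141795), and holds both if the cause is unclear. The drug-selection sentence in section 6.1.1 can serve as a model, although that section does not itself govern rash.

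The cost is one amended table line and one added sentence in the next amendment, with a short note to sites. Visits, sample size and analysis do not change.

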### 6.1.3 Trametinib Dose Modifications for Visual Changes

Trametinib is known to be associated with visual adverse events. An ophthalmologist should be consulted if changes in vision develop. However, if the visual changes are clearly unrelated to study treatment (e.g., allergic conjunctivitis), then monitor closely as it may be reasonable to defer ophthalmic examination. Special attention should be given to retinal findings (e.g., retinal pigment epithelial detachment (RPED) or retinovascular abnormalities (*i.e.*, branch or central retinal vein occlusions [RVO])). The ophthalmology exam will include best corrected visual acuity, visual field examination, tonometry, direct funduscopy, and indirect funduscopy. Optical coherence tomography is recommended at scheduled visits and if retinal abnormalities are suspected. Other types of ancillary testing including visual field examination, fundus photography, and fluorescein angiography may also be indicated as determined by clinical exam.

Guidelines regarding event management and dose reduction for visual changes considered to be related to study treatment are provided in the tables below.

Management and Trametinib Dose Modification for Visual Changes and/or Ophthalmic Examination Findings		
Event CTCAE Grade	Management Guideline	Dose Modification
Grade 1*	
 
Consult ophthalmologist within 7 days of onset.
 
	
 
If dilated fundus examination cannot be performed within 7 days of onset, hold trametinib until RPED and RVO can be excluded by retina specialist/ophthalmologist.
 
If RPED and RVO excluded, continue/or restart trametinib at same dose level.
 
If RPED suspected/diagnosed: See RPED dose modification table below (following this table); report as SAE.
 
If RVO diagnosed: Permanently discontinue trametinib and report as SAE.
 

Grade 2 and Grade 3	
 
Consult ophthalmologist immediately.
 
	
 
Hold trametinib
 
If RPED or RVO excluded, restart trametinib at same dose level after visual AE is <math>\leq</math> grade 1. If no recovery within 3 weeks, discontinue trametinib
 
If RPED diagnosed: See RPED dose modification table below; report as SAE.
 
If RVO: Permanently discontinue trametinib and report as SAE.
 

Grade 4	
 
Consult ophthalmologist immediately.
 
Report as SAE.
 
	
 
Hold Trametinib
 
If RPED/RVO excluded, may restart trametinib at same or reduced dose after discussion with the CTEP Medical Monitor.
 
If RVO or RPED, permanently discontinue trametinib.
 

Abbreviations: RPED = retinal pigment epithelial detachments; RVO = retinal vein occlusion; SAE = serious adverse event *If visual changes are clearly unrelated to study treatment (e.g., allergic conjunctivitis), monitor closely but ophthalmic examination is not required.		

Trametinib Dose Modification for RPED	
Event CTCAE Grade	Action and Dose Modification
Grade 1 RPED (Asymptomatic; clinical or diagnostic observations only)	
 
Continue treatment with retinal evaluation monthly until resolution. If RPED worsens, follow instructions below.
 

Grade 2-3 RPED (Symptomatic with mild to moderate decrease in visual acuity; limiting instrumental ADL)	
 
Interrupt trametinib.
 
Retinal evaluation monthly.
 
If improved to <math>\leq</math> Grade 1, restart trametinib with one dose level reduction (reduced by 0.5 mg) or discontinue in patients taking trametinib 1 mg daily.
 
If no recovery within 4 weeks permanently discontinue trametinib
 

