- *Retinal Pigment Epithelial Detachment (RPED)*: Also known as chorioretinopathy, RPED is a visual impairment due to fluid accumulation under the retina and causes blurry vision. There were five cases of RPED, previously termed central serous retinopathy, reported from the integrated trametinib safety population consisting of subjects treated with trametinib 2 mg once daily from five studies (Investigator's Brochure, 2013). As of 23 June 2013, 14 cases of RPED were reported across the entire trametinib program amongst subjects treated with trametinib either as monotherapy or in combination with other anti-cancer agents (including cases from a MEK/BRAF combination study).
- *Retinal vein occlusion (RVO)*: As of 23 June 2013, a total of four cases of RVO were reported across the entire trametinib program (including one case from a MEK/BRAF combination study) (Investigator's Brochure, 2013). All cases of RVO occurred in one eye only. Study drug was stopped at time of diagnosis in all cases. There was a decrease of visual acuity in two subjects with central RVO (CRVO) while the other two subjects had no meaningful decrease of visual acuity. In the two subjects with CRVO, local treatment with intravitreal injections of anti-VEGF antibodies was initiated within 2 weeks after RVO diagnosis, and visual acuity improved in one subject and restored to baseline conditions in another subject, at the time of the data cutoff. Three of these four cases were considered related to study treatment by the investigators.

Hepatic disorders: Abnormalities of liver enzymes and bilirubin have been observed with

administration of trametinib (Investigator's Brochure, 2013). However, assessment of these cases was often confounded by co-morbid conditions (such as biliary obstruction), concomitant use of other potentially hepatotoxic drugs, and liver metastases. At the 2 mg monotherapy dose, 8% to 34% of patients in five trials had LFT abnormalities. Of the 96 total patients (including crossovers) with LFT changes, the majority were grade 1 or 2 in severity (4% to 20% of all study patients); 26 had grade 3 events, and 6 patients had grade 4 events.

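### Section 6.1.3: after a grade 2-3 visual event, same-dose trametinib restart requires RPED *or* RVO to be excluded, where the grade 1 row requires both

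*Combined protocol and SAP*

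**What the plan says.** The visual-change table in section 6.1.3 has one row for grade 1, one for grades 2 and 3 together, and one for grade 4.

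- **Grade 1.** If the dilated fundus examination cannot be done within 7 days, the site is to "hold trametinib until RPED and RVO can be excluded by retina specialist/ophthalmologist". The restart rule is "If RPED and RVO excluded, continue/or restart trametinib at same dose level". RPED that is suspected or diagnosed goes to the separate RPED table; RVO means permanent discontinuation.
- **Grades 2 and 3.** The ophthalmologist is consulted immediately and trametinib is held. The restart rule is "If RPED or RVO excluded, restart trametinib at same dose level after visual AE is" grade 1 or lower, followed by "If no recovery within 3 weeks, discontinue trametinib". The later bullets begin "If RPED diagnosed", which leads to the RPED table, and with RVO, which means permanent discontinuation.
- **Grade 4.** Restart at the same or a reduced dose needs RPED/RVO (written with a slash) excluded and a discussion with the medical monitor.

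The RPED table, for grade 2-3 RPED that has improved to grade 1 or lower, says: "restart trametinib with one dose level reduction (reduced by 0.5 mg) or discontinue in patients taking trametinib 1 mg daily".

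**The concern.** The bullet is the operative rule for re-exposing a patient after a grade 2 or 3 visual event. It uses a different connective from the row above for the same decision, and the looser one goes with the more severe event. Taken at its word, excluding either diagnosis is enough.

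What is at stake is a restart dose that conflicts with the protocol's own instruction for the diagnosis still open. The RVO side is the more serious, because RVO calls for permanent discontinuation rather than a dose reduction. The trial is multicenter and sites work from the table as written, so the rule should not depend on each reader inferring the intent.

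**Working it through.** The plan states no figure on this point. The check sets the rows side by side and goes through the possible states.

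**1. States.** For each of RPED and RVO, the work-up can stand at excluded, open (neither diagnosed nor ruled out) or diagnosed. That gives 3 × 3 = 9 combinations. In 9 − (2 × 2) = 5 of them at least one condition is diagnosed, and the diagnosis-specific bullets of the grade 2-3 row govern. The other four depend on the restart bullet:

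| RPED | RVO | Restart condition met with *or* (grade 2-3 row) | Restart condition met with *and* (grade 1 wording) |
|---|---|---|---|
| excluded | excluded | yes | yes |
| open | excluded | yes | no |
| excluded | open | yes | no |
| open | open | no | no |

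The literal *or* admits three of the four, and *and* admits one. The two middle lines are the gap. Restart also needs the visual event to be back to grade 1 or lower, so the gap applies only to patients whose symptoms have recovered.

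**2. Do other bullets in the row catch the two middle lines?** No. The RPED bullet acts once RPED is diagnosed; unlike its grade 1 counterpart, it does not mention suspected RPED. The RVO bullet acts on RVO. A patient with an open question has only the hold and the restart bullet.

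**3. Dose consequence,** at the monotherapy levels in section 6.1:

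| Dose when held | Literal restart | If the open diagnosis is grade 2-3 RPED | If it is RVO |
|---|---|---|---|
| 2 mg | 2 mg | 2 − 0.5 = 1.5 mg | stop permanently |
| 1.5 mg | 1.5 mg | 1.5 − 0.5 = 1 mg | stop permanently |
| 1 mg | 1 mg | stop | stop permanently |

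**4. Frequency.** Section 2.2.1.3 says "There were five cases of RPED, previously termed central serous retinopathy, reported from the integrated trametinib safety population" (five studies at 2 mg) but gives no denominator. It reports four RVO cases across the whole program, also without one. The trametinib adverse event list in section 7.1.1.1, based on 968 patients, places both among rare events (below 3%). If that ceiling carried over (an assumption), expected diagnoses of each would be below 0.03 × 74 = 2.2 at maximum accrual and below 0.03 × 24 = 0.7 at minimum accrual. These are diagnoses of any grade. No document says how often a work-up settles one diagnosis and leaves the other open in a patient whose symptoms have recovered.

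**The case against.** The strongest case against is that this is copy-editing. Followed by one bullet for each diagnosis, the phrase reads naturally as meaning that neither was found. The same ophthalmic examination, with direct and indirect funduscopy, addresses both conditions, and the text adds: "Optical coherence tomography is recommended at scheduled visits and if retinal abnormalities are suspected". One diagnosis settled with the other left open should therefore be uncommon. Other safeguards exist: section 3.2.10 excludes patients with a history of, or predisposition to, either condition; the study calendar sends abnormal visual tests to an urgent full examination; and section 13.1 triggers a detailed safety review if more than 10% of subjects have RPED or RVO. Grade 1 is also not a uniformly strict comparator, since its hold applies only when the fundus examination is delayed, and the RPED table lets grade 1 RPED continue treatment.

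All of this stands as to likelihood and intent, and it keeps the point small. It does not make the two rows agree. Optical coherence tomography is recommended rather than required, so a first examination need not settle both questions.

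Two stronger readings should be resisted:

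- A reader might infer that a patient known to have RPED or RVO may restart at the same dose. The documents do not support that, because the later bullets of the same cell direct diagnosed RPED to the RPED table and stop the drug for RVO.
- A reader might infer that the grade 2-3 row is looser overall than grade 1. It is not: it has an immediate hold, immediate consultation, a recovery requirement and a 3-week limit. It is looser in two respects only, the connective and the missing mention of suspected RPED.

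**Conclusion.** The inconsistency is real and minor. Read literally, the grade 2-3 row permits a same-dose restart with one of the two diagnoses still open, contrary to what the protocol requires if that diagnosis is later made. The probable intent is that neither condition is present, and harm is unlikely given the hold and the consultation.

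The conclusion rests on a literal reading of one word and on the possibility that a work-up settles one diagnosis before the other. It does not rest on any rate. A reader might be tempted to supply one by deriving the size of the five trials from the diarrhea figures in section 2.2.1.3: 320/0.58 = 552 to 320/0.33 = 970 patients. The documents do not support relying on this. The count of about 320 is approximate and includes crossover subjects, the percentages may not include them, and the five trials are not said to be the five studies behind the RPED count. Even a sound RPED rate would not give the share of patients who reach the state in question.

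Nor does the point reach the primary analysis. Section 13.5.2 keeps patients with incorrect drug administration in the response rate, and no sample size, threshold or endpoint depends on this bullet.

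**What to change.** In the grade 2 and 3 row, change *or* to *and* in the restart bullet, so that same-dose restart requires both RPED and RVO to be excluded and the visual event to be grade 1 or lower. Keep the 3-week limit as it stands. A patient with an open diagnosis then simply remains on the hold already ordered by the first bullet, so the RPED trigger need not be extended to suspected cases and no dose is reduced on suspicion alone.

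Optionally, write *RPED and RVO* for the slash form in the grade 4 row. That row already requires discussion with the medical monitor, so less depends on it.

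The cost is one word in one cell at the next amendment. The clinical downside is that a recovered patient waits off drug until both diagnoses are excluded. The ophthalmology consultation already required covers both conditions, so the change adds no protocol-mandated visits or tests and no patients.
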